4.2.4 Additional exploratory endpoints

For all additional exploratory endpoints, the change from Visit 7 to Visit 10, Visit 9 to Visit 10 and Visit 10 to Visit 12 may also be evaluated. In addition, the change from Visit 1 to Visit 12 may also be investigated.

- SCAFI
- 9-HPT of dominant hand
- 8MWT
- SARA
- Health-related Quality of Life (EQ-5D-5L/Y)
- CGI-S by physician
- CGI-S by caregiver
- CGI-S by patient *if able*
- CGI-C by physician
- CGI-C by caregiver
- CGI-C by patient *if able*
- NPC-CSS
- Modified (5-domain) NPC-CSS

4.2.5 Safety endpoints

The safety parameters to be evaluated are:

- Adverse Events
- Laboratory safety measurements: haematology, clinical chemistry, urinalysis

- Vital signs
- ECGs
- Physical Examination

5 PARENT STUDY: STATISTICAL ANALYSIS

5.1 General considerations

The parent study is considered the study period between screening (Visit 0 or Visit 1) through Visit 6.

Raw data (in listings) will be presented in the same precision as received. Appropriate rounding will be performed for the following summary statistics, where applicable: mean, standard deviation (SD) and two-sided 90% confidence limits will be presented with at least one more decimal than the original data; minimum and maximum values will be presented with the same precision as the original data. In frequency tables, percentages will be presented with 1 decimal unless otherwise stated.

P-values will be presented with 3 decimals, and those smaller than 0.001 will be replaced by <0.001. One-sided p-values smaller than 0.05 will be considered statistically significant for the primary endpoint and indicative for other endpoints. No adjustment for multiple comparisons will be applied. Conclusions regarding treatment efficacy will not solely rely on detecting statistical significance but equal emphasis will be placed on the magnitude and clinical relevance of treatment differences as judged by the point estimates. All evaluations other than the primary endpoint will be considered exploratory in nature.

Descriptive statistics presented in general summary tables will be the number of non-missing observations (n), mean, SD, minimum, median and maximum for quantitative data. For categorical data, frequency counts and percentages will be determined.

In general, baseline is defined as the value measured prior to first study treatment administration (at Visit 2), unless otherwise specified. In case no value at Visit 2 is available, the value measured at Visit 1 will be used. A footnote may be added to those tables/listings presenting baseline value, with an explanation how this value was assessed.

If available in the database, data for screening failures will not be presented in summary tables, except for disposition, medical history and end-of-study displays. Data for screening failures will be listed as available.

A treatment emergent adverse event (TEAE) is defined as an adverse event that appears during or after study treatment and was absent before.

5.2 Adjudication of endpoint data

Each individual video (CI-S) or video pairing (CI-CS) will be read by two independent reviewers. For the CI-S assessments of the primary and non-primary anchor test, the independent raters will be given 6 videos of the patient's performance taken at Visit 1 to Visit 6. For the CI-CS assessments of the primary and non-primary anchor test, the raters will be given three pairs of videos and asked to score the CI-CS for each video pair. The video pairs

will be labeled Video A to Video B, Video B to Video C, and Video C to Video A¹. The videos will be presented in a random order, and the independent raters will be blinded to the timepoint corresponding to each video. The appropriate Likert scale score will be provided to each of the videos and pairs of videos.

For the CI-CS assessment, pairs of videos will be evaluated with the Likert scale defined as:

- Significantly Improved (Score = +3)
- Much Improved (Score = +2)
- Minimally Improved (Score = +1)
- No Observable Change (Score = 0)
- Minimally Worse (Score = -1)
- Much Worse (Score = -2)
- Significantly Worse (Score = -3)

If there is a scoring difference between the two blinded raters for a CI-CS assessment, the following rules will apply:

- If the difference between the blinded raters is 1, the two scores will be averaged, and the unrounded average value will be used for further analysis.
- If there is a scoring difference of >1 between the two blinded raters for a CI-CS assessment, then a third blinded rater will review the scores and will determine which score is more accurate (adjudication by consensus). The adjudicator's decision will be the final score for that video assessment and used for further analysis.

For the CI-S assessment, individual videos will be evaluated with the Likert scale defined as:

- Normal, not at all ill (Score = +3)
- Borderline ill (Score = +2)
- Mildly ill (Score = +1)
- Moderately ill (Score = 0)
- Markedly ill (Score = -1)
- Severely ill (Score = -2)
- Among the most extremely ill patients (Score = -3)

If there is any scoring difference between the two blinded raters for a CI-S assessment, the two scores will be averaged, and the unrounded average value will be used for further analysis.

Note that in averaging situations for the CI-CS and CI-S assessments, the scores may not fit the Likert scales as mentioned above. In case of average scoring present in the database, presentations will be on score only, without the additional description.

5.3 Missing data

Patients that withdraw from the study are replaced at the discretion of the sponsor. Data from withdrawal patients will be included in the analysis until their last assessment.

¹ [REDACTED] (2019). Video Review Charter. IntraBio Ltd. Internal Document.

For handling missing data of the statistical analyses applied to the primary and key secondary endpoints, refer to the respective analysis sections.

For other endpoints being presented with descriptive statistics only, such as baseline/screening data, safety presentations, additional secondary endpoints and (additional) exploratory endpoints, no imputation will be performed, unless otherwise specified (in the respective analysis section or in Section 10.1). All these analyses will be performed on data available at the visit considered. In summary tables, the number of patients without missing data will be presented (per visit, if applicable) unless otherwise specified. In calculations of percentages, subjects with missing data will not be considered in numerator or denominator unless otherwise specified.

Using the most conservative approach, missing/incomplete information related to AEs will be handled as listed below, to indicate an AE as being treatment emergent or presented having a certain intensity/causality. Note that the imputed dates or intensity/causality will not appear in data listings, but only in descriptive statistics tables (where applicable).

- In case of (partially) missing onset dates, the AE will be handled as follows:
 - If full start date is available, and on or after first dosing date, the AE is considered treatment emergent.
 - In case full stop date is available and prior to first dosing date, the AE is considered prior.
 - If the day part of the start date is missing:
 - The AE is considered treatment emergent if the month and year of the start date are the same or after the month and the year of the first dosing date.
 - If the day and month part of the start date are missing:
 - The AE is considered treatment emergent if the year of the start date is the same or after the year of the first dosing date.
 - In case the start date is completely missing:
 - If stop date is fully available and on or after the first dosing date, the AE is considered treatment emergent.
 - If the stop date is partially missing, but the month and year (or year alone in case of missing month) are after the month and year (or year alone) of the first dosing date, the AE is considered treatment emergent.
 - In case full start date and full stop date are missing, the AE is considered treatment emergent.
- In case intensity is missing for a certain TEAE, this will be regarded as severe.
- In case causality is missing for a certain TEAE, this will be regarded as related.
- In case seriousness is missing for a certain AE, this is discussed and addressed prior to database lock and unblinding in agreement with the sponsor and data management provider.

Regarding prior/concomitant medication, a similar approach will be followed for partially missing dates, as will be done for AEs as described above. If a comedication is started and stopped prior to the first date of study treatment (i.e. first dosing date), this is considered prior.

Based on the BDRM, certain values can be decided to be excluded from analyses. These values will be listed, but not included in descriptive statistics, plots or statistical analyses. This may be outlier data that are a result of unambiguous measurement errors.

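### For an AE with no start date and a partial stop date, the SAP 5.3 rule leaves out the tie with first dosing, so a tied AE meets no treatment-emergent condition

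*SAP*

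**What the plan says.** SAP 5.3 opens its AE date rules with a principle: "Using the most conservative approach, missing/incomplete information related to AEs will be handled as listed below". The rules then run as follows.

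- Full start date: treatment emergent if on or after first dosing.
- Start date with day missing: "The AE is considered treatment emergent if the month and year of the start date are the same or after" those of first dosing.
- Start date with day and month absent: "The AE is considered treatment emergent if the year of the start date is the same or after the year of the first dosing date".
- Start date missing, full stop date: "If stop date is fully available and on or after the first dosing date, the AE is considered treatment emergent".
- Start date missing, partial stop date: treatment emergent if the stop month and year "or year alone in case of missing month) are after the month and year (or year alone) of the first dosing date".
- Neither date: "In case full start date and full stop date are missing, the AE is considered treatment emergent".

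One rule classes an AE as prior from its stop date, and it needs a complete date: "In case full stop date is available and prior to first dosing date, the AE is considered prior". No default is given for an AE that meets none of these.

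SAP 5.7.1 builds the tables by SOC and PT, severity and relationship on TEAEs. It also asks that the AE listing separate prior from treatment-emergent events. SAP 6.3 reuses the approach in the Extension Phase with the first Extension dose as reference, and treats events that began in the Parent Study and continue as prior.

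**The concern.** The rule for a missing start with a partial stop is the only one that uses a strict inequality. A partial stop date in the same month or year as first dosing does not show that the event ended before dosing. This is the ambiguous case in which a conservative rule should lean towards treatment emergent.

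The result is also illogical. An AE with no dates at all is treatment emergent. Adding a partial stop date that is compatible with treatment takes that status away, and completing the date to a day on or after first dosing restores it.

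What is at stake is the content of the TEAE tables. SAP 5.3 also words its conservative defaults for missing intensity (severe) and missing causality (related) for TEAEs, so a tied AE would not receive those either. In the listing it is neither prior nor treatment emergent, and a programmer would have to choose.

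**Working it through.** The plan states no figure that depends on this rule, so there is none to reproduce. The check sets the rules side by side and then illustrates the size.

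**Step 1: what each rule does with a tie.**

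| Start date | Stop date | Condition | Tie |
|---|---|---|---|
| Full | any | ≥ first dose | treatment emergent |
| Day missing | any* | month/year ≥ | treatment emergent |
| Day and month missing | any* | year ≥ | treatment emergent |
| Missing | Full | ≥ first dose | treatment emergent |
| Missing | Partial | month/year, or year, **>** | **no rule met** |
| Missing | Missing | none | treatment emergent |

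*Unless a full stop date before first dosing makes the AE prior.

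**Step 2: worked cases.** Take a first dose on 15 June 2020 (illustrative) and a missing start date.

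| Stop date recorded | SAP as written | With 'same as or after' |
|---|---|---|
| 15 Jun 2020 | treatment emergent | unchanged |
| Jun 2020 | no rule met | treatment emergent |
| 2020 | no rule met | treatment emergent |
| Jul 2020, or 2021 | treatment emergent | unchanged |
| Dec 2019, or 2019 | not treatment emergent | unchanged |
| none | treatment emergent | unchanged |

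**Step 3: illustrative share of on-study stops that tie.** Protocol 3.1.5 gives about 84 days from first dose to the final washout visit. The other inputs are assumptions, not from the documents: first doses uniform over the 366 days of 2020, and true stop dates uniform over the H days from first dose.

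- Year only: share = 1 − ((H − 1)/2)/366. For H = 84: 1 − 41.5/366 = 0.887.
- Month and year: a month of L days holds L(L + 1)/2 tied pairs of first dose and stop. Over 2020 that is 7 × 496 + 4 × 465 + 435 = 5,767. For H = 84: 5,767/(366 × 84) = 5,767/30,744 = 0.188.

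Varying the window over treatment only (42 days), treatment with its 7-day allowance (49), and treatment plus washout with both allowances (98):

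| H (days) | Month and year known | Year only |
|---|---|---|
| 42 | 38% | 94% |
| 49 | 32% | 93% |
| 84 | 19% | 89% |
| 98 | 16% | 87% |

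**Step 4: after the change.** The share of on-study stops missed falls to 0%. The price is paid on records that truly ended before dosing. If their stop dates are assumed uniform over the 14 days before first dose, 75% of month-and-year and 98% of year-only records would now be called treatment emergent.

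**The case against.** Several points on the other side stand.

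- The SAP nowhere says that a tied AE is not treatment emergent. It leaves the AE unclassified. The stated principle points towards inclusion, and SAP 10.1 allows unforeseen conventions to be settled when met and documented. Absence from the TEAE tables follows from applying the rule literally; it is not an instruction.
- The trigger may never occur. Protocol 6.2.1 has start and stop dates recorded for each AE and AEs asked about at every visit, and Protocol 9.2 repeats queries until they are resolved.
- The percentages are not misclassification rates. AEs are recorded from consent, and a TEAE must have been absent before treatment, so an AE that stops soon after first dose may have begun before it.

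One defence does not stand. The rule for both dates missing could be read to cover a partial stop date, which would rescue the tied AE. That reading makes the preceding rule redundant, and it would make an AE that ended a year before dosing treatment emergent. SAP 10.1, in its diagnosis-date conventions, uses nearly the same phrase for a wholly absent date, as distinct from a partial one.

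A reader might also infer wider damage, which the documents do not support.

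- Serious AEs: the overview row in SAP 5.7.1 is not limited to TEAEs, and SAEs and deaths have their own listings.
- Incidence rates: these are defined on AE cases per treatment or washout cycle. An AE with no start date and a year-only stop usually could not be placed in a cycle even after the change.
- Concomitant medication: SAP 5.3 says only that partial dates are handled in a similar way, and it calls a medication prior only if it both started and stopped before first dosing. A tie does not establish that.
- Listing only: that provision concerns AEs that start before dosing, and a tied AE has no known start.

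**Conclusion.** The defect holds as an error in one rule. The strict inequality contradicts the principle stated at the head of the list and every neighbouring rule, and a tied AE is left neither treatment emergent nor prior. Applied literally, the tables by SOC/PT, severity and relationship would omit it, though it would remain in the listing of all AEs.

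The effect is confined to AEs with a completely missing start date and a partial stop date. The documents do not say how many there will be, and there may be none. Within that group the 84-day figures of about 89% and 19% show that ties would be common, but only under uniform first-dose and stop dates. They cannot be read as the proportion of TEAEs lost, and the documents do not support a claim that the trial's TEAE count is materially understated. No efficacy analysis or sample size is affected. This is a minor correction.

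**What to change.** In SAP 5.3, in the rule for a missing start date with a partial stop date, replace 'are after' with 'are the same as or after'. Stop dates in an earlier month or year then stay outside, as now.

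Confirm in SAP 6.3 that the same tie handling applies against the first Extension dose, and that AEs known to have started in the Parent Study remain prior. This needs saying because Extension dosing can begin one day after Visit 6, so a Parent Study AE with no start date could tie with the first Extension dose.

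The cost is a few words before database lock. An occasional AE that ended before dosing will be counted as treatment emergent, which is the direction the SAP has already chosen.

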5.4 Interim analysis

Per-patient data listings and summary tables/plots will be provided for the several DSMB meetings and as specified in the DSMB Charter.

A limited draft analysis prior to database lock of the Parent Study is scheduled as indicated by an NTF created by IntraBio.

There will be an analysis of the primary, secondary, and exploratory endpoints relating to the Parent phase once Visit 6 has been completed, and an interim CSR will be written.

5.5 Baseline characteristics

5.5.1 Inclusion/exclusion criteria

An individual patient listing of the deviations from inclusion and exclusion criteria will be presented.

5.5.2 Demographics

Demographic data at baseline will be summarized for all patients and by the 4 age/weight/dosing groups in tabulations.

Appropriate descriptive statistics for age, height, weight, BMI, ethnic group and sex will be given. The summary will be created for each analysis population separately. Additionally, demographic data will be listed.

5.5.3 Baseline characteristics

The following relevant patient baseline characteristics will be listed and summarized overall (frequency and percentage) and are considered key subgroups. The subgroups differentiated on a median value will use the median value as determined for the specific analysis population.

- Naïve versus non-naïve as determined at screening
- Age (paediatric versus adult)
- Age/weight/dosing group
- Region (US versus EU)
- Selected Primary Anchor Test (9HPT-D or 8MWT)
- Patients on miglustat vs Patients not on miglustat at baseline visit (Visit 1 and/or Visit 2)
- Composite of SARA Subtests 1- 4 (Gait, Stance, Sitting, Speech): classification based on below (\leq)/above the median value at Visit 1.
- Intra-Patient variability between SARA score at Visit 1 (Baseline 1) vs Visit 2 (Baseline 2): classification based on below (\leq)/above the median value of the difference between the two visits.

- Intra-Patient variability between CI-S score (for primary anchor only) Visit 1 (Baseline 1) vs Visit 2 (Baseline 2): classification based on below (\leq)/above the median value of the difference between the two visits.
- Age of diagnosis: Early-infantile (<2 years), Late-infantile (2 to $<$ 6 years), Juvenile (6 to $<$ 15 years), Adolescent/Adult (\geq 15 years)
- Disease severity: classification based on below (\leq)/ above the median SARA score at Visit 1.

5.5.4 Disposition

A summary table will be created, stating the number of patients per site, including site number, location/country, and investigator.

To present disposition, a summary of all included, randomised, treated and completed patients will be created. Number/percentage screened will be included as well (if available in the database). Additionally, in the same summary, the number/percentage of patients in the SAF, mITT and PPS will be presented. Furthermore, the frequency and percentage per reason for non-completion will be added.

Additionally, a listing displaying all disposition information (including reasons for withdrawal and reasons for exclusion from the analysis population, if available electronically) on a per patient level will be created. This listing will include follow-up time for each patient, calculated from date of first dose until end of study for the parent phase.

5.5.5 Medical history

Medical history will be tabulated per System Organ Class (SOC) and Preferred term (PT) according to the Medical Dictionary for Regulatory Activities (MedDRA) terminology list and presented as number/percentage of patients in each SOC and PT for the SAF. SOC and PT will be presented in descending order of frequency of occurrence based on SOC and PT. These data will also be listed on a per patient level.

NPC specific history will be summarized as appropriate, presenting confirmed diagnosis (yes/no) and time since diagnosis. For calculation of time since diagnosis, see Section 10.1.

NPC specific history data as collected will also be listed on a per patient level.

5.5.6 Pregnancy data

Pregnancy test result data will be listed for females of childbearing potential only, on a per visit basis.

5.5.7 Other screening data

Other data collected at screening and/or baseline only, if available, will be listed. These screening/baseline data will be presented using all subjects included in the study, if applicable.

5.6 Statistical analysis efficacy endpoints

The primary analysis population is the mITT for the primary and all secondary endpoints. Analyses of these endpoints based on the PPS will also be undertaken to provide supplementary information on efficacy. The ITT population will be used only for baseline summary tables.

Analyses of the primary endpoint based on the mITT population will utilise a last observation carried forward (LOCF) approach for missing/unreadable videos at Visit 5 and Visit 6. For the primary endpoint CI-CS, this implies that the CI-CS value for Visit 4 to Visit 6 will be assigned the value 0 (stable) if both videos at Visit 5 and Visit 6 are unavailable.

Also, for the key secondary endpoint, Change in Severity Score based on Averaged Clinical Impression of Severity (CI-S), it is assumed that if both videos are missing/unreadable for the baseline (Videos from Visit 1 or 2), treatment (Videos from Visit 3 or 4), or washout (Videos from Visit 5 or 6) period, the average change from one period to another will be assigned the value 0 (stable).

A sensitivity analysis for missing data will be performed for the statistical analyses to compare patient's outcome on the primary outcome measure and their compliance throughout the study. The robustness of the primary analyses in the mITT analysis set will be assessed as follows:

- If either video for Visit 3 or Visit 4 is available but both videos for Visit 5 and Visit 6 are not available, then the value -1 (worsening) will be used instead of 0 for the CI-CS for Visit 4 to Visit 6 unless the missingness is due to a technical reason (MCAR, e.g. due to machine failure).

For each of the primary and secondary endpoints there will be separate descriptive statistical displays within the key subgroups as listed in Section 5.5.3 without any statistical analysis. For the subgroup presentations, only the mITT population will be used. Spaghetti plots will not be created for the subgroup analyses; these will be presented in forest plots (one for each endpoint, excluding the SARA -, SAFI - and mDRS subscores and excluding the EQ-5D-5L/Y), presenting the mean or (pseudo-)median with a 90% two-sided CI, using a stem at mean or median difference of 0, where applicable. Upon discretion of the programmer, the forest plots may be presented as two plots: one for Visit 4 versus Visit 2 and one for Visit 6 versus Visit 4.

Considering the number of subgroups, the forest plots may become unclear and indecipherable. When that occurs, a split will be made into two forest plots for the endpoints: one for the first 7 subgroups, and one for the remaining.

All individual primary and secondary endpoint data will be listed as well.

